4. SUBJECT DISPOSITION

4.1. Subject Enrollment and Disposition

A summary of subject enrollment will be provided by treatment group for each country, investigator within a country, and overall. The summary will present the number and percentage of subjects in the Safety Analysis Set. For each column, the denominator for the percentage calculation will be the total number of subjects analyzed for that column.

A summary of subject disposition will be provided by treatment group. This summary will present the number of subjects screened, the number of subjects enrolled, the number of subjects enrolled but never treated, and the number and percentage of subjects in each of the categories listed below. For the “Treated” category, the denominator for the percentage calculation will be the total number of subjects enrolled for each column. For all other categories, the denominator for the percentage calculation will be the total number of subjects in the Safety Analysis Set for each column.

- Treated (Safety Analysis Set)
- In FAS
- In PK Analysis Set
- Completed study treatment
- Did not complete study treatment with reasons for premature discontinuation of study treatment
- Completed the study
- Did not complete the study with reason for premature discontinuation of study

Among subjects who completed study treatment and who discontinued study treatment, the number and percentage of subjects will be summarized for:

- Who had no HCV posttreatment Week 4 assessment and thereafter (No HCV FU-4 and thereafter)
- Who had HCV posttreatment Week 4 assessment but no HCV posttreatment Week 12 assessment and thereafter (With HCV FU-4 but No FU-12 and thereafter)

If a subject did not have any HCV RNA assessment ≥ 21 days after the last dose of any study drug (i.e. lower bound of FU-4 visit for HCV RNA data), the subject is categorized as having “No HCV FU-4 and thereafter”. If a subject had the HCV FU-4 assessment but did not have any HCV RNA assessment ≥ 70 days after the last dose of any study drug (i.e. lower bound of FU-12 visit for HCV RNA data), the subject is categorized as having “With HCV FU-4 but No FU-12 and thereafter”.

In addition, the total number of subjects who were enrolled, and the number of subjects in each of the disposition categories listed above will be displayed in a flowchart.

The following by-subject listings will be provided by subject ID number in ascending order to support the above summary tables:

- Disposition for subjects who complete study treatment and study
- Disposition for subjects who did not complete study treatment and/or study with reasons for premature discontinuation of study drug and/or study
- Lot number and kit ID (if applicable)

4.2. Extent of Exposure

Extent of exposure to study regimen and individual study drug will be examined by assessing the total durations of study regimen and individual study drug exposure and the level of adherence to any study drug and individual study drug specified in the protocol.

4.2.1. Durations of Exposure to Study Regimen and Individual Study Drug

Total duration of exposure to study regimen will be defined as last dose date of any study drug minus first dose date of any study drug plus 1, regardless of any temporary interruptions in study drug administration, and will be expressed in weeks using up to 1 decimal place (e.g. 4.5 weeks). Total duration of exposure to individual study drug will be defined as last dose date of individual study drug minus first dose date of individual study drug plus 1, regardless of any temporary interruptions in study drug administration.

The total durations of exposure to study regimen and individual study drug will be summarized using descriptive statistics (n, mean, SD, median, Q1, Q3, minimum, and maximum) and using the number (i.e. cumulative counts) and percentage of subjects exposed through the following time periods: Baseline (Day 1), Week 1 (Day 7), Week 2 (Day 14), Week 4 (Day 28), Week 8 (Day 56), and Week 12 (Day 84) for all subjects and additionally Week 16 (Day 112), Week 20 (Day 140), and Week 24 (Day 168) for subjects receiving 24 weeks of treatment. Summaries will be provided by treatment group for the Safety Analysis Set.

4.2.2. Adherence to Study Drug

The level of adherence to individual study drug will be assessed separately based on the total amount of individual study drug administered relative to the total amount of individual study drug prescribed. In this study, SOF 400 mg tablets, SOF 100 mg tablets, and SOF 50 mg capsules containing granules have been used. For RBV, both REBETOL capsules and REBETOL RBV oral solution have been used. Each capsule contains 200 mg RBV and the oral solution contains 40 mg RBV per mL.

Given the fact that multiple formulations of the study drug have been used in this study, the adherence will be calculated based on the amount of SOF (mg) or RBV (mg) by the following formula:

$$\text{Level of Adherence(\%)} = \left(\frac{\text{Total Amount of Study Drug Administered}}{\text{Total Amount of Study Drug Prescribed at baseline}} \right) \times 100$$

Where the presumed total amount of study drug (mg) administered to a subject will be determined by the data collected on the drug accountability eCRF using the following formula:

$$\text{Total Amount of Study Drug (mg) Administered} = \left(\sum \text{Total Amount of Study Drug (mg) Dispensed} \right) - \left(\sum \text{Total Amount of Study Drug (mg) Returned} \right)$$

Note: If calculated adherence is greater than 100%, the result will be set to 100%.

The total amount of prescribed SOF (mg) for 12 weeks and 24 weeks are as follows:

Age Group and Body Weight	SOF Daily Dose	Total Amount of SOF Prescribed for 12 Weeks	Total Amount of SOF Prescribed for 24 Weeks
12 to <18 years any weight	400 mg/day	33600 mg	67200 mg
6 to <12 years any weight	200 mg/day	16800 mg	33600 mg
3 to <6 years weighing ≥17 kg	200 mg/day	16800 mg	33600 mg
3 to < 6 years weighing <17 kg	150 mg/day	12600 mg	25200 mg

RBV was prescribed by weight at baseline for all subjects. The total amount of RBV (mg) prescribed for 12 weeks and 24 weeks is as follows:

Body Weight kg (lbs.)	RBV Daily Dose	RBV Number of Capsules	Total Amount of RBV Prescribed for 12 Weeks	Total Amount of RBV Prescribed for 24 Weeks
<47 (<103)	15 mg/kg/day	Use Oral Solution. Divided dose in the morning and evening.	1,260 mg/kg	2,520 mg/kg
47-49 (103-108)	600 mg/day	1 × 200-mg capsules A.M. 2 × 200-mg capsules P.M.	252 capsules (50400 mg)	504 capsules (100800 mg)
50-65 (110 – 143)	800 mg/day	2 × 200-mg capsules A.M. 2 × 200-mg capsules P.M.	336 capsules (67200 mg)	672 capsules (134400 mg)
66-80 (145 – 176)	1000 mg/day	2 × 200-mg capsules A.M. 3 × 200-mg capsules P.M.	420 capsules (84000 mg)	840 capsules (168000 mg)
81-105 (178-231)	1200 mg/day	3 × 200-mg capsules A.M. 3 × 200-mg capsules P.M.	504 capsules (100800 mg)	1,008 capsules (201600 mg)
>105 (>231)	1400 mg/day	3 × 200-mg capsules A.M. 4 × 200-mg capsules P.M.	588 capsules (117600 mg)	1,176 capsules (235200 mg)

Note: Subjects with a body weight greater than or equal to 47 kg may utilize the RBV oral solution if necessary.

Weight reported as a decimal number was rounded to the whole number to determine the prescribed RBV dosage. For example, a subject weighing 49.5 kg fell into the 50-65 kg category and received 800 mg/day.

Subjects who prematurely discontinue study drug for lack of efficacy (i.e. virologic failure) will have the total amount of study drug prescribed calculated up to the first date when virologic failure criteria were met. For virologic failure confirmed by 2 consecutive measurements the date of the first measurement will be used. If there are study drug bottles dispensed on or after the subject first met virologic failure criteria, these bottles will not be included in the calculation of adherence. If a bottle is dispensed and the bottle is returned empty, then the number of tablets returned will be entered as zero. If a bottle is dispensed but not returned (missing), the number of tablets taken from that bottle will be counted as zero.

Descriptive statistics for the level of adherence (n, mean, SD, median, Q1, Q3, minimum, and maximum) with the number and percentage of subjects belonging to adherence categories (e.g. < 80%, ≥ 80 to < 90%, ≥ 90%) will be provided by treatment group for the Safety Analysis Set. No inferential statistics will be provided for duration of exposure and adherence to study drug. Categorical displays will be provided for the number of subjects who are at least 80% adherent to individual study drug and study regimen (i.e. adherence is ≥ 80% for each of the study drugs). No inferential statistics will be provided.

A separate by-subject listing of study drug administration and drug accountability will be provided by subject ID number (in ascending order) and visit (in chronological order).

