**Table 7-1. RBV Dose Reduction Guidelines**

Laboratory Values	Reduce RBV Dose by 200 mg/day if:	Discontinue RBV if:
Hemoglobin in subjects with no cardiac disease	<10 g/dL	<8.5 g/dL
Hemoglobin in subjects with history of stable cardiac disease	≥2 g/dL decrease in hemoglobin during any 4 week period treatment	<12 g/dL despite 4 weeks at reduced dose

Dose reduction in pediatric patients is accomplished by modifying the recommended RBV dose from original starting dose of 15 mg/kg daily in a two-step process to 12 mg/kg/day, then to 8 mg/kg/day, if needed.

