### 7.2. Subject Stopping Rules for SOF

The Gilead Medical Monitor should be consulted prior to dose discontinuation of SOF unless the investigator believes that immediate action is warranted to ensure the continued safety of the subject.

Administration of SOF may be discontinued due to a clinical or laboratory event. There is no option for SOF dose reduction. If SOF is stopped for toxicity, it should not be restarted, RBV should be stopped and the subject should complete an Early Termination Visit.

Subjects who meet any of the following laboratory criteria must stop treatment with SOF and RBV:

- Elevation of ALT and/or AST >5x Day 1 or nadir, confirmed by immediate repeat testing
- Abnormal elevation of ALT >3x Day 1 and total bilirubin >2 x ULN, confirmed by immediate repeat testing
- Confirmed elevation of ALT >15 x ULN
- Any Grade 3 or greater rash associated with constitutional symptoms
- Any Grade 4 event or lab abnormality assessed as related to treatment with SOF

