3.4. Examination of Subject Subsets

The efficacy endpoint SVR12 will be analyzed for the following subsets:

- sex (male, female)
- race (black, non-black)
- ethnicity (hispanic or latino, non-hispanic or latino)
- baseline HCV RNA ($< 800,000$ IU/mL, $\geq 800,000$ IU/mL)
- baseline weight (\leq median, $>$ median)
- baseline ALT ($\leq 1.5 \times$ ULN, $> 1.5 \times$ ULN)
- IL28B (CC, non-CC [further broken down to CT, TT])
- prior HCV treatment experience (treatment naive, treatment experienced)
- Interferon (IFN) eligibility (IFN-eligible, IFN-ineligible)
- most recent response to prior HCV treatment (non-response, relapse/breakthrough, IFN-intolerant) for treatment experienced subjects
- study treatment status (completed study treatment, discontinued study treatment)
- adherence to study regimen ($< 80\%$, $\geq 80\%$).

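### RBV adherence is measured against the full-course amount prescribed at baseline, so a child who takes every dose as instructed can be classed under 80% adherent after a protocol-directed RBV change

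*SAP*

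**What the plan says.** SAP 4.2.2 takes milligrams dispensed minus milligrams returned and divides by the "Total Amount of Study Drug Prescribed at baseline". It states that "RBV was prescribed by weight at baseline for all subjects" and tabulates fixed totals for 12 and 24 weeks. The one adjustment to the prescribed amount is for subjects who stop early because of virologic failure. Nothing is said about RBV reduced, interrupted or stopped for toxicity.

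Protocol Table 7-1 has a column headed "Reduce RBV Dose by 200 mg/day if" and another headed "Discontinue RBV if", both driven by hemoglobin. A sentence under the table takes the pediatric dose from 15 mg/kg daily "in a two-step process to 12 mg/kg/day, then to 8 mg/kg/day, if needed". For the other drug, Protocol 7.2 says "There is no option for SOF dose reduction", so the dose-reduction problem concerns RBV only.

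Under SAP 4.2.2 a subject is adherent to the regimen only if each drug reaches 80%. SAP 3.4 lists "adherence to study regimen" (<80%, ≥80%) among the SVR12 subsets. SAP 6.1.4 gives point estimates, exact intervals and a forest plot for each treatment group within each subset.

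**The concern.** The denominator does not follow the prescription. When RBV is lowered under Protocol 7.1, the amount the child is supposed to take falls but the amount it is compared with does not. Because each drug must reach 80%, a low RBV figure alone puts the child in the under-80% stratum, even with perfect SOF intake.

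That stratum can then mix children who missed doses with children managed as the protocol directs. A reader of the forest plot would take the row as evidence about missed doses when part of it may reflect RBV tolerability. The cells are small: about 100 subjects are divided by age group and genotype before the adherence split, so one or two reclassified children can shift an estimate.

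Reductions are foreseeable. Protocol 4.2 admits females with hemoglobin from 11 g/dL, and Table 7-1 triggers reduction below 10 g/dL in subjects without cardiac disease.

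**Working it through.** **Inputs.** Daily doses and course totals come from SAP 4.2.2, and reduction steps from Protocol Table 7-1 and the sentence below it. The course length T is 12 or 24 weeks. The timing of each change is my assumption. Every child below takes every instructed dose unless stated.

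**The SAP's own denominators.** 15 mg/kg × 84 days = 1,260 mg/kg and 15 × 168 = 2,520 mg/kg, as printed. For capsules, 600 × 84 = 50,400 mg and 600 × 168 = 100,800 mg, also as printed. These are full-course amounts at the starting dose.

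**First step only.** From Day 1 the score is 12/15 = 80.0%, which falls in the ≥80% class. After Week 4 it is (4×15 + 8×12)/(12×15) = 86.7%, or (4×15 + 20×12)/(24×15) = 83.3%. A fully compliant child who starts on 15 mg/kg is never below 80% on this step alone.

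**Both steps.** With t12 weeks at 12 mg/kg and t8 weeks at 8 mg/kg, the score is 1 − (3·t12 + 7·t8)/(15·T). It is below 80% only when 3·t12 + 7·t8 > 3·T.

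| Course | 12 mg/kg from | 8 mg/kg from | Score |
|---|---|---|---|
| 12 weeks | Week 4 | Week 8 | (60+48+32)/180 = 77.8% |
| 12 weeks | Week 4 | Week 10 | (60+72+16)/180 = 82.2% |
| 24 weeks | Week 4 | Week 8 | (60+48+128)/360 = 65.6% |
| 24 weeks | Week 8 | Week 16 | (120+96+64)/360 = 77.8% |
| 24 weeks | Week 12 | Week 16 | (180+48+64)/360 = 81.1% |

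**RBV stopped.** The score is the fraction of the course completed, so it is below 80% if RBV stops before 80% of the course. Stopping at Week 8 gives 8/12 = 66.7% or 8/24 = 33.3%.

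**A 200 mg/day cut from D mg/day.** The score is 1 − 200f/D, where f is the fraction of the course at the lower dose. It is below 80% only when f > D/1000.

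| Starting dose | Cut at Week 4 of 12 | Cut at Week 4 of 24 | Below 80% if cut before about |
|---|---|---|---|
| 600 mg/day | 5,600/7,200 = 77.8% | 10,400/14,400 = 72.2% | Day 34 of 84, Day 67 of 168 |
| 800 mg/day | 8,000/9,600 = 83.3% | 15,200/19,200 = 79.2% | Day 17 of 84, Day 34 of 168 |
| 1,000 mg/day or more | ≥80% | ≥80% | never |

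A later cut can also be harmless at the lowest capsule dose: from 600 mg/day at Week 8 of 12 the score is (8×600 + 4×400)/7,200 = 88.9%.

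**First step plus a few missed doses.** At an assumed 95% true compliance, a first step after Week 4 gives 0.833 × 0.95 = 79.2% of a 24-week course, but 0.867 × 0.95 = 82.3% of a 12-week course.

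**Comparison.** If the denominator follows the prescribed dose, every fully compliant child above scores 100%, and the child with 95% compliance scores 95%.

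**A related inconsistency.** The 200 mg/day column and the mg/kg sentence in Protocol 7.1 give different reduced doses for the same child. At 30 kg the starting dose is 450 mg/day. The column gives 250 mg/day (55.6% of the start) and the first mg/kg step gives 360 mg/day (80.0%). The classification therefore also depends on which passage a site follows.

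**The case against.** A reader might infer that any child whose RBV is reduced will be classed under 80%. The documents do not support that. The first pediatric step lands exactly on 80.0% at worst, the cut-off is inclusive, and several two-step paths stay above it (82.2%, 81.1%). From 1,000 mg/day or more, a 200 mg/day cut never crosses the line. The outcome depends on timing and starting dose.

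A reader might also infer that the efficacy conclusion is at risk. It is not. SVR12 by adherence is one of twelve descriptive subsets with estimates and intervals only, adherence is summarised without inference, and the test in SAP 6.1.3 does not use it.

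RBV tolerability is also visible elsewhere. SAP 7.1.6 tabulates adverse events leading to RBV modification, interruption or discontinuation, and SAP 4.2.2 lists drug administration by subject. A careful reader could trace the affected children from these.

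All of this stands, and it limits the size of the point. It does not remove the point: separate tables do not correct the composition of the under-80% row. The SAP already shortens the denominator when treatment stops for lack of efficacy, so leaving out toxicity is a gap in a principle it has accepted.

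**Conclusion.** The concern holds in a limited form. Under SAP 4.2.2 a fully compliant child can be classed under 80% adherent after an RBV change made under Protocol 7.1. That requires one of the following:

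- enough time on the second mg/kg step;
- RBV stopped before 80% of the course;
- an early 200 mg/day cut from 600 or 800 mg/day.

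A first step combined with a few missed doses can have the same effect on a child whose true compliance is well above 80%.

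In the examples that cross the line with no missed dose, scores run from 79.2% (800 mg/day cut at Week 4 of 24) down to 33.3% (RBV stopped at Week 8 of 24). These rest on assumed timings. The documents give no rate of RBV reduction, so the number of children affected cannot be computed and may be none or a few. The consequence is confined to the adherence summary and the descriptive SVR12 subgroup. It is worth correcting because the output is labelled adherence and could be read as something else.

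**What to change.** In SAP 4.2.2, calculate the RBV denominator from the amount prescribed over time, including protocol-directed reductions, interruptions and RBV discontinuation. Use that figure for the 80% categories and for the SAP 3.4 subgroup. Report the amount taken over the amount planned at baseline separately, labelled RBV dose intensity.

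The cost is SAP wording and slightly more derivation from dosing records. Protocol 9.5.1 and SAP 3.7.1 refer to a study drug administration form, Protocol 10.1.5 requires the dose regimen in source records, and SAP 7.1.6 already relies on RBV modifications being identified. The eCRF itself is not among the documents, so the sponsor should confirm that it records each prescribed RBV change with a date.

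Separately, the 200 mg/day column of Protocol Table 7-1 and the two-step mg/kg sentence below it must be reconciled.

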4.3. Protocol Deviations

A summary of important protocol deviations will be provided by the Clinical Operations group for subjects in the Safety Analysis Set.

Subjects who received study drug other than their enrolled treatment assignment will be listed with the start and stop dates that they received incorrect study treatment.

5. BASELINE CHARACTERISTICS

5.1. Demographics

Subject demographic variables (i.e. age, sex, race, and ethnicity) will be summarized by treatment group and total in each age group using descriptive statistics (n, mean, SD, median, Q1, Q3, minimum, and maximum) for age, and using the numbers and percentages of subjects for sex, race, and ethnicity. Age is calculated in years at the date of initial study drug administration. If a subject did not receive study drug after enrollment, the subject's age will be calculated from the date that the subject signed the informed consent form. The summary of demographic data will be provided for the Safety Analysis Set.

A by-subject demographic listing will be provided by subject ID number in ascending order.

In addition, demographic variables (i.e. age, sex, race, and ethnicity) will be summarized by treatment group defined in [Table 3-2](#) and total for 3 to < 6 years of age subjects.

5.2. Other Baseline Characteristics

Other baseline characteristics include:

- weight in kg
- height in cm
- body mass index (BMI; in kg/m²)
- HCV genotype (2, 3 with both genotypes further broken down to observed subtypes)
- cirrhosis (presence, absence, unknown)
- IL28B (CC, CT, TT)
- baseline HCV RNA (log₁₀ IU/mL) as a continuous variable and as categories (< 800,000 IU/mL, ≥ 800,000 IU/mL)
- baseline ALT (U/L) as a continuous variable and as categories (≤1.5 × ULN, > 1.5 × ULN)
- estimated glomerular filtration rate (eGFR) using Schwartz Formula (mL/min/1.73m²)
- prior treatment experience (treatment naïve, treatment experienced)
- IFN eligibility (IFN-eligible, IFN-ineligible)
- most recent response to prior HCV treatment (non-response, relapse/breakthrough, IFN-intolerant) for treatment experienced subjects

- mode of HCV Infection
- bone age in years
- Tanner Stage

Estimated Glomerular Filtration Rate (GFR) will be calculated using Schwartz Formula ($\text{mL}/\text{min}/1.73\text{m}^2 = k \times L/\text{Scr}$) [(k is a proportionality constant, for adolescent females ≥ 12 years old is 0.55; for adolescent males ≥ 12 years old is 0.70, and for children 3- <12 years old is 0.55); L is height in centimeters (cm); and Scr is serum creatinine (mg/dL)]

These baseline characteristics will be summarized by treatment group and total in each age group using descriptive statistics (n, mean, SD, median, Q1, Q3, minimum, and maximum) for continuous variables and using the numbers and percentages of subjects for categorical variables. The summary of baseline characteristics will be provided for the Safety Analysis Set.

A by-subject listing of other baseline characteristics will be provided by subject ID number in ascending order.

In addition, baseline characteristics will be summarized by treatment group defined in [Table 3-2](#) and total for 3 to < 6 years of age subjects.

5.3. Swallowability Assessment

Swallowability of SOF tablets will be summarized using the numbers and percentages of subjects in each of the swallowability categories (as applicable) by total in 12 to < 18 years of age group and 6 to < 12 years of age group respectively.

A by-subject listing of Swallowability of SOF tablets will be provided by subject ID number in ascending order.

5.4. Palatability of SOF Oral Granules

Palatability of SOF oral granules will be summarized using the numbers and percentages of subjects who took SOF oral granules in each of palatability categories by total in each age group (as applicable).

A by-subject listing of Palatability of SOF oral granules will be provided by subject ID number in ascending order.

5.5. Medical History

General medical history (ie, conditions not specific to the disease being studied) data will be collected at screening and listed only. General medical history data will not be coded. A by-subject listing of disease-specific medical history will be provided by subject ID number (in ascending order) and medical history of abnormalities (in chronological order).

6. EFFICACY ANALYSES

6.1. Key Efficacy Endpoint

6.1.1. Definition of the Key Efficacy Endpoint

The key efficacy endpoint is SVR12 defined as HCV RNA < LLOQ (i.e. < 15 IU/mL) 12 weeks after discontinuation of all study drugs in the FAS. The COBAS[®] AmpliPrep/COBAS[®] TaqMan[®] HCV Test, v2.0 for use with the High Pure System will be used to measure HCV RNA.

